62 daily BG, frequency of hypoglycemia, length of hospital stay and complications. Similarly, the
63 use of GLP-1 and its analogues have also been shown to improve glycemic control and to have a
64 beneficial cardiovascular profile improving functional status and endothelial function (21),
65 increasing left ventricular function in patients with heart failure (22) and in surgery patients
66 undergoing CABG (22, 23), and to reducing infarct size and preserving left ventricular
67 myocardial performance in ischemic models (24).

68

69 Liraglutide is a once-daily human GLP-1 analogue approved for the treatment of T2D.
70 Liraglutide has been shown to lower blood glucose, stimulate endogenous insulin secretion,
71 decrease plasma glucagon levels, inhibit gastric emptying, reduce food intake and body weight
72 and improve β -cell function when administered subcutaneously (25). Liraglutide increases
73 insulin secretion in a glucose-dependent manner (i.e., only when plasma glucose levels are
74 elevated), resulting in low-risk of hypoglycemia when used as monotherapy. When compared to
75 insulin glargine therapy, the use of GLP1 has resulted in comparable reduction in HbA1c level,

76 lower rates of hypoglycemia and less weight gain (26). No prospective studies; however, have
77 compared the efficacy and safety of liraglutide in the hospital setting or after hospital discharge.
78
79

80 **SPECIFIC OBJECTIVES:**

81 Primary objective is to compare the safety and efficacy of liraglutide (Victoza®) versus glargine
82 insulin on glycemic control after 26 weeks of treatment in medicine and surgical patients with
83 T2D after hospital discharge.
84

85 **RESEARCH DESIGN AND METHODS**

86 **Study Hypothesis (hypotheses):**

87 We hypothesize that treatment with liraglutide (Victoza®) will result in a similar improvement in
88 HbA1c levels and in lower rate of hypoglycemic events compared to treatment with glargine
89 (Lantus®) in patients with T2D after hospital discharge.
90

91 **Specific Aim 1: To determine whether treatment with liraglutide (Victoza®) will result in**
92 **similar glycemic control (HbA1c at 26 weeks) and a lower rate of hypoglycemic events**
93 **compared to treatment with glargine (Lantus®) in patients with T2D after hospital**
94 **discharge.** Patients with poorly controlled (HbA1c $\geq 7\%$ -10%) T2D treated with diet or oral
95 antidiabetic agents, or on low-dose insulin therapy (TDD ≤ 0.4 unit/kg/day) will be randomized
96 to liraglutide or glargine with or without oral agents at hospital discharge.
97

98 **Endpoints:**

99 **Study Outcomes:**

100 The primary outcome of the study is to determine differences in HbA1c concentration at 26
101 weeks from discharge between liraglutide and glargine insulin therapy.
102

103 The secondary outcome is to compare differences between treatment groups in any of the
104 following measures during the 26 weeks following hospital discharge in patients with T2D:

- 105 • Self-measured blood glucose (SMBG) 7-point profiles
- 106 • Fasting and postprandial BG concentration
- 107 • Incidence rate and number of hypoglycemic events (<70 mg/dl) and severe hypoglycemic
108 events (<40 mg/dl).
- 109 • Percent of patients with 26 week HbA1c $<7.0\%$ and no hypoglycemia
- 110 • Percent of patients with 26 week HbA1c $<7.0\%$ and no weight gain
- 111 • Percent of patients with 12 week HbA1c $<7.0\%$ and no hypoglycemia
- 112 • Change in body weight and BMI

- 113 • Cardiovascular risk factors including changes in blood pressure, heart rate, and lipid
- 114 profile.
- 115 • Total daily dose of insulin
- 116 • Number of emergency room visits and hospital readmissions
- 117 • Acute renal failure during the 26-week follow-up defined as a clinical diagnosis of acute
- 118 renal failure with documented new-onset abnormal renal function (increment in
- 119 creatinine ≥ 0.5 mg/dL from baseline)

120
121

122 **Study type:**

123 The trial is a 26-week, randomized, open label-controlled two-armed, multi-center, multi-
124 national trial investigating the efficacy and safety of liraglutide versus glargine insulin in
125 medicine and surgical patients with T2D after hospital discharge.

126 We will recruit a total of 330 poorly controlled (HbA1c $\geq 7\%$ -10%) patients with T2D treated
127 with diet or oral antidiabetic agents (OAD) or on low-dose insulin therapy (TDD ≤ 0.4
128 unit/kg/day) prior to admission. Patients will be treated with a standard basal bolus insulin
129 regimen during the hospital stay. Prior to hospital discharge, patients will be randomized to
130 liraglutide or glargine with or without oral antidiabetic drugs. After discharge, a member of the
131 diabetes research team will contact patients via telephone call every 2 weeks to assess response
132 to therapy. In addition, patients will be asked to attend an outpatient clinic visit at 2 (optional), 4,
133 12 and 26 weeks after hospital discharge. Recommendation on insulin dose adjustment will be
134 provided to patients at each telephone contact and clinic visits.

135
136 Recommendation for liraglutide dose escalation will be done every one or two weeks until the
137 maintenance dose of 1.8 mg is reached. Dose escalation can be extended over 2 weeks at the
138 discretion of the investigator in case of gastrointestinal adverse events. Liraglutide and insulin
139 will be add-on to the subject's pre-admission OAD regimen. Dose of OAD should remain
140 unchanged throughout the trial, however dose reduction of insulin and sulfonylurea is allowed
141 due to hypoglycemia.

142
143
144 **Study Groups:**

145 We plan to analyze a total of 280 patients (who receive study medication) with T2D at the time
146 of hospital discharge.

- 147
- 148 • Group 1. Liraglutide once daily in combination to OADs (n=140).
- 149
- 150 ▪ Group 2. Glargine once daily in combination to OADs (n=140).

151
152

153 **Study population:**

154 This will analyze 380 general medicine and surgical patients with a known history of T2D, age
155 18-80, treated with diet alone and/or oral antidiabetic agents including sulfonylureas, repaglinide,
156 nateglinide, DPP4s, SGLT2, or metformin as monotherapy or in combination therapy or on low-
157 dose insulin therapy (TDD ≤ 0.4 unit/kg/day) prior to admission. Subjects will be recruited from 5
158 medical centers in the United States. A total of 300 patients will be recruited at Grady Memorial
159 Hospital, Emory University Hospital and Emory Midtown hospital.

161 **Study Sites:** This study will be performed at Grady Memorial Hospital, Emory University
162 Hospital, Emory University Hospital at Midtown, and 3 institutions in the United States:

- 163 1. MetroHealth Medical Center, Cleveland (PI: [name].)
- 164 2. State University of NY at Buffalo (PI: [name].)
- 165 3. University of Miami, Florida (PI: [name].)
- 166 4. Sanatorio Guemes, Buenos Aires -Argentina (PI: [name])

169 **Inclusion Criteria**

- 170 1. Males or females between the ages of 18 and 80 years discharged after hospital admission
171 from non- ICU general medicine and surgical services (excluding gastrointestinal and
172 cardiac surgeries).
- 173 2. Admission HbA1c between 7% and 10%
- 174 3. Patients with T2D treated with diet alone or with oral antidiabetic agents as monotherapy or in
175 combination therapy (excluding GLP1 receptor agonists) or on low-dose insulin therapy
176 (TDD ≤ 0.4 unit/kg/day) prior to admission.
- 177 4. Subjects with a hospital admission BG < 400 mg/dL without laboratory evidence of diabetic
178 ketoacidosis (serum bicarbonate < 18 mEq/L or positive serum or urinary ketones).
- 179 5. BMI > 25 Kg/m² and ≤ 45 Kg/m²

181 **Exclusion Criteria**

- 182 1. Age < 18 or > 80 years.
- 183 2. Subjects with stress hyperglycemia (BG > 140 mg/dL and HbA1c < 6.5%)
- 184 3. Subjects with a history of type 1 diabetes (1).
- 185 4. Treatment with GLP1 analogs during the past 3 months prior to admission.
- 186 5. Recurrent severe hypoglycemia or hypoglycemic unawareness.
- 187 6. Subjects with gastrointestinal obstruction, gastroparesis or those expected to require
188 gastrointestinal suction.
- 189 7. History of medullary thyroid cancer or multiple endocrine neoplasias
- 190 8. Patients with acute or chronic pancreatitis, pancreatic cancer or gallbladder disease.
- 191 9. Patients with clinically significant hepatic disease (cirrhosis, jaundice, end-stage liver
192 disease, portal hypertension) and elevated ALT and AST > 3 times upper limit of normal, or
193 significantly impaired renal function (GFR < 30 ml/min).

- 194 10. Treatment with oral or injectable corticosteroid (equivalent or higher than prednisone
195 5mg/day), parenteral nutrition and immunosuppressive treatment.
196 11. Mental condition rendering the subject unable to understand the nature, scope, and possible
197 consequences of the study.
198 12. Female subjects who are pregnant or breast-feeding at time of enrollment into the study.
199 13. Females of childbearing potential who are not using adequate contraceptive methods (as
200 required by local law or practice).

201

202 **Investigational drugs.**

203

- 204 • Liraglutide 6.0 mg/mL solution for subcutaneous (s.c.) injection. The solution will be
205 provided in 3 mL prefilled pen.
- 206 • Liraglutide will be provided to patients
- 207 • Glargine will be provided

208

209

210 **Withdrawal Criteria**

211

- 211 1. The subject may withdraw at will at any time.
- 212 2. The subject may be withdrawn from the trial at the discretion of the investigator due to a
213 safety concern or if judged non-compliant with trial procedures or included in contravention
214 to the inclusion and/or exclusion criteria.
- 215 3. Subject diagnosed with acute pancreatitis by clinical and/or radiographic criteria.
- 216 4. If the fasting BG and average daily BG on 3 consecutive days exceeds > 15.0 mmol/L (240
217 mg/dL). If this occurs, the subject will be called for an unscheduled visit as soon as possible.
218 A confirmatory FPG should be obtained and analyzed by the hospital laboratory. If this FPG
219 exceeds 15.0 mmol/L (240 mg/dL), and no treatable intercurrent cause for the hyperglycemia
220 has been identified, the subject must be withdrawn.
- 221 5. Pregnancy or intention to become pregnant.

222 **Subject Replacement**

223 There will be no replacement of subjects in this trial.

224

225 **Rationale for Study Population**

226 We will recruit patients with poorly controlled T2D (HbA1c \geq 7%-10%) treated with diet and/or
227 oral antidiabetic agents or on low-dose insulin therapy (TDD \leq 0.4unit/kg/day)prior to admission.
228 Patients will be treated with a basal bolus insulin regimen during the hospital stay (standard of
229 care). Prior to hospital discharge, patients will be randomized to receive liraglutide or glargine
230 as monotherapy in treatment of patients treated with low-dose insulin therapy (TDD \leq 0.4
231 unit/kg/day) (or as add-on therapy to the subject's pre-admission OAD regimen.

232

233 We plan to analyze a total of 280 patients (who receive study medication) with T2D at the time
234 of hospital discharge [liraglutide once daily in combination to OADs (n=140) or glargine once
235 daily in combination to OADs (n=140)].
236

237 **GROUP 1. Liraglutide Treatment Group.**

238

239 **▪ Patients receiving no Therapy prior to admission:**

- 240 • Discharge on liraglutide once daily.
 - 241 • Start metformin if A1C \geq 8% and no contraindications.
- 242

243 **▪ Patients receiving OAD prior to admission:**

- 244 • If no contraindication, restart pre-admission OADs according to standard of care and
245 investigator's medical discretion (metformin, sulfonylureas, nateglinide, repaglinide,
246 pioglitazone) in combination to liraglutide.
 - 247 • The total daily dose of insulin secretagogues (sulfonylureas, nateglinides and
248 repaglinide) will be reduced to 50% of pre-admission dose to avoid risk of
249 hypoglycemia.
 - 250 • DPP4-inhibitors will not be used in combination with liraglutide during the study
251 period.
- 252

253 **Liraglutide Titration:**

254 Liraglutide will be administered once daily in accordance with a 3-4 week dose escalation
255 regimen with weekly increments of 0.6 mg until the maintenance dose of 1.8 mg is reached.
256 Liraglutide will be administered once daily by s.c. injections, either in the abdomen, thigh or
257 upper arm. Injections can be done at any time of the day and irrespective of meals. It is
258 recommended that the time of injection is consistent throughout the trial. Subjects will be
259 instructed to perform an air shot before the first use of a new prefilled pen.
260

261 **GROUP 2. Glargine Group**

262

263 **V.e. Treatment recommendations at discharge:**

264

265 **▪ Patients receiving no Therapy prior to admission:**

- 266 • Discharge on glargine once daily at 50% of total hospital dose
 - 267 • Add metformin if A1C \geq 8% and no contraindications.
- 268

269 **▪ Patients receiving OAD prior to admission:**

270

271

272

- If no contraindication, restart pre-admission OADs according to standard of care and investigator’s medical discretion (metformin, sulfonylureas, repaglinide, nateglinide, pioglitazone) in combination to glargine at 50% of hospital dose.
- The total daily dose of insulin secretagogues (sulfonylureas, nateglinides and repaglinide) will be reduced to 50% of pre-admission dose to avoid risk of hypoglycemia.
- DPP4-inhibitors will not be used in combination with liraglutide during the study period

Algorithm for outpatient glargine insulin dose adjustment:

Insulin Glargine	
If mean FBG > 180 mg/dL for the last 2 consecutive days and no episodes of hypoglycemia (BG <70 mg/dL)	Increase daily dose by 4 IU
If mean FBG > 140 mg/dL for the last 2 consecutive days and no episodes of hypoglycemia (BG <70 mg/dL)	Increase daily dose by 2 IU
If mean FBG between 100 to 140 mg/dL for the last 2 consecutive days and no episodes of hypoglycemia (BG <70 mg/dL)	No Change
If any FBG between 70 – 99 mg/dl	Decrease by 4 IU or 10% of total daily dose
If any FBG or RBG < 70 mg/dl	Decrease by 8 IU or 20% of total daily dose
If any FBG or RBG < 40 mg/dl	Decrease total daily dose by 30%

In hospital Diabetes Education. Prior to discharge, participants will be trained on:

1. Diabetes education if not received within 1 year of admission.
2. ADA targets for fasting and premeal BG between 70 to 130 mg/dL.
3. Use of glucose meters for home glucose self-monitoring (meters may vary at different institutions).
4. Keeping BG records, and will receive a log-book to record glucose tests results.
5. Hypoglycemia recognition and management (see VI.B.)
6. Insulin administration (if needed).

Follow-up Care:

- If baseline visit was not fully completed at the time of discharge, patients will be scheduled to return for a short in-person visit to complete (body measurements) study procedures within 7 days of discharge. Research team will call to verify correct administration of study medication and availability of medications and glycemic control monitoring supplies.

- 300 • After discharge, a member of the diabetes research team will contact patients via
301 telephone call every 2 weeks for a total of 26 weeks.
- 302 • Patients will be asked to attend the next outpatient clinic visit at 4 weeks of hospital
303 discharge. During this visit, patients will receive 8 weeks drug supply of liraglutide and
304 will be asked to return to clinic at 12 weeks for the next outpatient visit. During this visit,
305 patients will receive 12 weeks (3 months) drug supply of liraglutide and will be asked to
306 return to a fourth and final visit at 26 weeks of hospital discharge.
- 307 • Recommendations on insulin adjustment will be provided to patients at each telephone
308 and clinic visits by a licensed physician (fellow or study physician) (see section Vf).

309 **During follow up we will collect the following information:**

- 310 1. Glycemic control:
- 311 a. Mean daily fasting and premeal blood glucose levels.
- 312 b. HbA1c at 3 and 6 months of discharge
- 313 c. Number of hypoglycemic events
- 314 - **Symptomatic hypoglycemia** is defined as an event with typical symptoms (i.e.,
315 sweating, palpitation, and feeling of hunger) with or without confirmation by
316 plasma glucose <70 mg/dl (3.9 mmol/L).
- 317 - **Severe hypoglycemia** is defined as episodes necessitating assistance and
318 associated with measured plasma glucose < 40 mg/dl (2.2 mmol/L) or with
319 prompt recovery after administration of carbohydrates, glucagon, or other
320 resuscitative actions. These episodes may be associated with sufficient
321 neuroglycopenia to induce seizure or coma. Blood glucose measurements may
322 not be available during such an event, but neurological recovery attributable to
323 the restoration of BG to normal is considered sufficient evidence that the event
324 was induced by low plasma glucose.
- 325
- 326 2. Diabetes treatment:
- 327 a. Number of patients receiving insulin therapy, dosage and compliance.
- 328 b. Use of liraglutide and other oral agents, dosage and compliance.
- 329 c. Protocol adherence by PCP (diabetes clinic versus PCP)
- 330
- 331 3. Clinical Outcome:
- 332 a. Hospital readmissions
- 333 b. Emergency room visits
- 334
- 335
- 336

337 **7-point self-measured blood glucose profile:**

338 Subjects will be instructed to perform a 7-point SMBG profile three times during the trial within
339 one week prior to site visit on a day where the subject do not anticipate unusual strenuous
340 exercise.

341 **Time-points for 7-point profile:**

342
343 The blood glucose levels should be measured and recorded in the diary (including date, actual
344 clock time and blood glucose value) at the following time points, always starting with
345 measurement before breakfast.

- 346
- 347 • Before breakfast
- 348 • 90 min after the start of breakfast
- 349 • Before lunch
- 350 • 90 min after the start of lunch
- 351 • Before dinner
- 352 • 90 min after the start of dinner
- 353 • At bedtime
- 354
- 355

356 **Body measurements**

357 Body measurements consist of the parameters: Body weight, height, waist circumference, hip
358 circumference and BMI

359 **Body weight:** Body weight should be measured in kilogram or pound, without shoes and only
360 wearing light clothing.

361 **Height:** Height (without shoes) should be measured in centimeters or inches and recorded
362 without decimals.

363 **Waist and hip circumference:** The waist circumference is defined as the minimal abdominal
364 circumference located midway between the lower rib margin and the iliac crest. The hip
365 circumference is defined as the widest circumference around the buttocks. Three consecutive
366 measurements of waist and hip circumference should be taken and recorded. Mean values will
367 be used for result analysis. The waist and hip circumferences will be measured to the nearest 0.5
368 cm (0.2 inches) using a non-stretchable measuring tape.

369 The subject should be measured in a standing position with an empty bladder and wearing light
370 clothing with accessible waist and hip. The tape should touch skin, but not compress soft tissue
371 and twist in tape should be avoided. The subject should be asked to breathe normally and the
372 measurement should be taken when the subject is breathing out gently.

373 **Body Mass Index (BMI):** BMI will be calculated by the formula Body weight (Kg)/m².

374

375

376

377

378 **Assessment for Safety**

379
380
381
382
383
384
385
386
387
388
389
390
391
392
393
394
395
396
397
398
399
400
401
402
403
404
405
406
407
408
409
410
411
412
413
414
415
416
417
418
419

Potential Risks to the Subjects:

Hypoglycemia. It is possible that following the proposed protocol, patients receiving basal insulin or liraglutide may develop hypoglycemia. For the purpose of this analysis we **symptomatic hypoglycemia** is defined as an event with typical symptoms (i.e., sweating, palpitation, and feeling of hunger) with or without confirmation by plasma glucose <70 mg/dl (3.9 mmol/L). We expect that approximately 20% to 40% of subjects treated with basal insulin alone or in combination to OADs will experience one or more episodes of hypoglycemia during follow-up. We anticipate that less than 10% of patients taking liraglutide alone or in combination to OADs will experience hypoglycemic events.

Severe hypoglycemia is defined as episodes necessitating assistance and associated with measured plasma glucose < 40 mg/dl (2.2 mmol/L) or with prompt recovery after administration of carbohydrates, glucagon, or other resuscitative actions. These episodes may be associated with sufficient neuroglycopenia to induce seizure or coma. Blood glucose measurements may not be available during such an event, but neurological recovery attributable to the restoration of BG to normal is considered sufficient evidence that the event was induced by low plasma glucose. We anticipate that less than 5% of patients on insulin or liraglutide alone or in combination to OADs will experience severe hypoglycemic events.

Gastrointestinal side effects including nausea and vomiting are more common in patients treated with liraglutide compared to placebo. The frequency of nausea and vomiting is reported in up to 14% of patients receiving higher doses of liraglutide 1.8 mg in combination to metformin and sulfonylurea therapy compared to 3.5% in patients receiving placebo plus OADs (Victoza package insert). The number of adverse events will be collected at each telephone contact or clinic visit. There have been few reported events of acute pancreatitis. Subjects should be informed of the characteristic symptoms of acute pancreatitis: persistent, severe abdominal pain. If pancreatitis is suspected, liraglutide and other potentially suspect medicinal products should be discontinued. If the investigator suspects acute pancreatitis, all suspected drugs should be discontinued until confirmatory test have been conducted and appropriate treatment should be initiated. Subjects diagnosed with acute pancreatitis (as a minimum 2 of 3: characteristic abdominal pain, amylase and/or lipase >3xUNR or characteristic findings on CT scan/ MRI should be withdrawn from the study.

Protection against Risks:

We will follow safeguards to minimize the risk to our subjects: a) we will carefully monitor response to medical treatment every 2 weeks by telephone contact and every 3 months during clinic visits, b) women of reproductive age who are sexually active will undergo a urine pregnancy tests prior to participation in the study, c) female subjects whom are pregnant, breast-feeding, or not willing to use appropriate contraception at time of enrollment will not be included in the study, d) patients with significant comorbidities such as chronic kidney disease

420 greater than stage III, liver cirrhosis, gastroparesis, and pancreatic disorders will be excluded
421 from the study.

422
423 Hypoglycemia: Patients will receive diabetes education prior to discharge and will be instructed
424 on hypoglycemia sign/symptoms and treatment. Patients will be asked to call the diabetes center
425 and/or PCP in the event of hypoglycemia. If a patient develops hypoglycemia, the dose of OAD
426 will be reduced or discontinued and the daily dose of basal insulin will be reduced by 10% to
427 30% (see treatment algorithm).

428 Gastrointestinal side effects including nausea and vomiting may be expected, more commonly in
429 patients treated with liraglutide. In subjects with suspected acute pancreatitis liraglutide and
430 other potentially suspect medicinal products should be discontinued until confirmatory tests have
431 been conducted and appropriate treatment initiated.

432
433
434

STATISTICAL CONSIDERATIONS:

435 This study is randomized multicenter, open-label controlled trial. The overall hypothesis is that
436 patients with T2D discharged on liraglutide and glargine will experience similar improvement in
437 glycemic control (HbA1c level at 26 weeks post-discharge). In addition, we anticipate that
438 compared to patients treated with insulin glargine, patients on liraglutide will experience lower
439 number of hypoglycemic events and less weight gain during follow-up.

440

441 **Sample Size and Power Calculations:** The primary endpoint in this study is glycemic control
442 measured by HbA1c at 26 weeks after discharge between treatment groups. To show the non-
443 inferiority of liraglutide to basal glargine insulin in terms of glycemic control, we set the
444 equivalence margin as 0.5%, from a view that an HbA1c difference < 0.5% is usually not
445 considered as clinically significant.

446 Based on preliminary discharge data, we assume the standard deviation of 26 week A1c is
447 bounded about 1.5%. We set the margin of equivalence as 0.5% and assume the true difference
448 between mean A1c is 0. A sample size of 124 for each treatment group would achieve 80%
449 power to reject the hypothesis that the mean HbA1c in patients treated with liraglutide is < 0.5%
450 more than that in patients treated with glargine based on a two-sample one-sided t test, with
451 alpha=0.05. Accounting for 10% attrition rate, we would need 140 patients per treatment group.
452 This leads to a final total sample size estimate of 280 patients that receive study medication.

453

454 The secondary outcome of major interest in this study is the difference in hypoglycemia (BG <70
455 mg/dl). Based on our preliminary discharge data, 30-40% of patients treated with basal insulin
456 will have at least one hypoglycemia episode. Assuming a hypoglycemia rate of 20-35% in the
457 insulin group in this study, given the sample size of 140 subjects per treatment group, based on a
458 two sided Fisher's exact test with alpha=0.05, we would have 80% power to detect an odds ratio
459 in hypoglycemia rate of 0.42 in liraglutide group (versus glargine group). In the following table,

460 we give the estimated power under different assumed group differences in hypoglycemia rate,
461 represented by four hypothesized odds ratios.

462 Table: Estimated power with 140 subjects per group (before 10% attrition) and the anticipated
463 hypoglycemia rate of 35% in the insulin group based on two-sided Fisher's exact test with
464 alpha=0.05.
465

Odds Ratio	0.2	0.3	0.4	0.5
Power	>0.99	0.97	0.85	0.64

466
467 The above calculations show that we will have a good chance to achieve over 80% power for the
468 secondary outcome of hypoglycemia rate.
469

470
471

472 **Analysis of Primary Endpoint:**

473 The primary endpoint in this study is glycemic control measured by HbA1c concentration at 26
474 weeks post-discharge. We will first compare the primary outcome using two-sample t-tests (or
475 Wilcoxon tests) or one-way ANOVA, followed by multivariate linear regression to estimate and
476 test the difference between the two treatment groups while simultaneously accounting for other
477 potential confounders. Particularly, we will investigate center effect for the HbA1c outcome by
478 stratified univariate analysis or multivariate linear regression. Transformations will be applied if
479 normality violation is detected. Stepwise, backward, or forward model selection strategy will be
480 adopted to determine the variables to be included in the final model. Standard diagnostic and
481 model checking procedures will be applied to examine the fit of the developed models.
482

483 **Analysis of Secondary Endpoints:**

484 Secondary endpoints in this study include rate of hypoglycemia, number of hypoglycemia
485 events, change in body weight in kilograms, number of episodes of severe hyperglycemia,
486 complications and Emergency Room or hospital readmissions. For hypoglycemia outcomes, we
487 will first conduct nonparametric comparisons of the rate of hypoglycemia based on a two-sided
488 Chi-square test (or Fisher's exact test in the presence of low incidence rates), followed by the
489 Cochran-Mantel-Haenszel test which adjusts for the potential center effect. Univariate Poisson
490 regression (or Negative Binomial regression) will be performed to assess whether there is any
491 difference in the number of hypoglycemia events between the two treatment groups. We will
492 further conduct multivariate Logistic regression, Poisson regression (or negative binomial

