526 obtained before any trial related procedures including screening procedures. The consent form,
527 potential risks and benefits, and the rights of research participants will be explained to the
528 participant by the investigators or research coordinator. Individuals will be asked if they have
529 questions, and a member of the research staff will answer questions. The principal investigator
530 will also be available at all times to answer questions that participants may have during the
531 consent procedure or during the time a participant is enrolled in the study. The consent form will
532 be completed in accordance with the IRB guidelines of Emory University. A signed copy of the
533 consent form will be provided to the participant and a copy will be placed in the file that is
534 maintained for each participant in the study office.
535

536 Informed consent will follow the procedure of Emory University Institutional Review Board.
537 Every potential participant will be informed in writing and verbally with the important and key

538 points of the study. One of the investigators or research coordinators will obtain a witnessed
539 informed consent prior to inclusion of a patient into the study.

540

541 The study will be conducted in accordance with the Declaration of Helsinki and will be
542 conducted in accordance with the ICH GCP guidelines. The sponsor-investigator will comply
543 with all applicable regulatory and legal requirements, ICH GCP guidelines and the Declaration
544 of Helsinki in obtaining and documenting the informed consent.

545

546 **STUDY SCHEDULE:**

FIRST PATIENT IN	2014 FEBRUARY
SCREENING	~2000
RANDOMIZED	280
LAST PATIENT RECRUITED	2020 MAY
LAST PATIENT IN (COMPLETED)	2020 DECEMBER
DATA ANALYSIS	DECEMBER 2020-JANUARY 2021
SUBMISSION TO CONGRESS OR JOURNAL	ADA 2021 MAJOR MEDICINE JOURNAL AND/OR DIABETES CARE

547

548 Flow Chart

Visit Type	Baseline Visit Hosp-prior to D/C	TC	Clinic visit	TC	TC	TC	Clinic visit	TC	TC	TC	TC	TC	TC	Clinic visit
Time-wks. ¹	0	2	4	6	8	10	12	14	16	18	20	22	24	26
Inf. consent	x													
Incl/excl criteria	x													
Random	x													
Withdrawal criteria		x	x		x		x		x		x		x	
Drug Compliance		x	x	x	x	x	x	x	x	x	x	x	x	x
Dose adjustment		x	x	x	x		x			x		x		x
Efficacy														
Vital signs	X		x				x							x
Phys Exam	X		x				x							x
Body wgt	x		x				x							x
Body measurements	X ²		x				x							x
BMI	x		x				x							x
HbA1c	X ³						x							x
Fasting BG	X ³		x				x							x

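### The analysed set is defined by receipt of study drug in an open-label trial, and the conflicting totals (280, 330, 380) leave the share of randomised patients it could omit undetermined

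*Combined protocol and SAP*

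**What the plan says.** All references are to the combined protocol and SAP.

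- **Analysed.** Study Groups states "We plan to analyze a total of 280 patients (who receive study medication) with T2D at the time" of discharge, with 140 per arm; Rationale for Study Population repeats this. Sample Size and Power Calculations concludes "This leads to a final total sample size estimate of 280 patients that receive study medication". Study population gives a different figure: "This will analyze 380 general medicine and surgical patients with a known history of T2D, age" 18 to 80.
- **Recruited.** Study type: "We will recruit a total of 330 poorly controlled" patients. Study population adds that 300 will be recruited at three local hospitals.
- **Randomised.** The Study Schedule lists "SCREENING ~2000" and "RANDOMIZED 280".
- **Replacement.** Subject Replacement: "There will be no replacement of subjects in this trial".
- **Timing and blinding.** Study type places randomisation before discharge. Randomization and Blinding describes an open-label trial with the allocation table mailed to each site.
- **Analysis sets.** The primary and secondary endpoint sections name no intention-to-treat or other set. They give no rule for patients randomised but never treated. Withdrawal Criteria allows the investigator to withdraw patients for non-compliance or ineligibility, and no section says whether those patients stay in the analysis.

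**The concern.** Randomisation protects the comparison of all patients assigned to each arm. A set defined by receipt of drug is usually defended on the ground that blinding makes starting treatment unrelated to the arm. That defence is not available here, because patient and staff can know the assignment before the first dose. The arms are two injectable treatments with different expected side effects, so a difference in starting is plausible, though the documents do not show one.

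If non-starters differ between arms and are left out, the week-26 HbA1c comparison, hypoglycaemia, readmissions and emergency visits are no longer strictly randomised comparisons. The conflicting totals add two problems. The reader cannot tell how large the omitted group could be, and the number at which enrolment stops is not fixed.

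**Working it through.** **1. The plan's own sample size.** Inputs from Sample Size and Power Calculations: SD 1.5, margin 0.5, true difference 0, one-sided alpha 0.05, power 80%.

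n per arm = 2 × SD² × (1.645 + 0.842)² / margin² = 2 × 2.25 × 6.18 / 0.25 ≈ 111.3, so 112. The exact noncentral t calculation also gives 112.

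The stated 124 is not reproduced. It may already contain attrition, since 112 × 1.10 = 123.2, which rounds up to 124. The next step does follow: 124 / 0.9 = 137.8, so 138 per arm, and the plan uses 140 (280 in total). The gap between 112 and 124 is a separate matter. It errs towards more patients and does not support this point.

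**2. Do the totals fit together?**

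- 280 randomised, none replaced, 280 treated: possible only if every randomised patient receives drug.
- 280 randomised, 380 analysed: impossible.
- 330 recruited, 280 randomised: possible if some consented inpatients leave before randomisation. The plan does not say when a patient counts as recruited.
- 300 recruited at three hospitals: more than 280, so if the 280 is right, recruited cannot mean randomised.

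**3. Share of randomised patients outside a treated set of 280.**

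| Randomised total | Left out | Share |
|---|---|---|
| 280 (the only figure labelled randomised) | 0 | 0% |
| 330 (if all recruited are randomised) | 50 | 50/330 = 15.2% |
| 380 (if that figure is the randomised total) | 100 | 100/380 = 26.3% |

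**4. What differential non-starting could do (assumed inputs).** The documents give no rates. Suppose non-starters are 5 to 10 percentage points more frequent in one arm, and their week-26 HbA1c would be 0.5 to 1.5 percentage points higher than that of starters. Omitting them shifts the difference by

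shift = (difference in non-starting) × (excess HbA1c),

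that is, from 0.05 × 0.5 = 0.025 to 0.10 × 1.5 = 0.15, or 5% to 30% of the 0.5 margin. With equal arms, a 10-point difference needs at least 5% non-starters overall (10% in one arm, none in the other). If all 280 randomised patients receive drug, the shift is zero.

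As an illustration, take a shift of 0.10 in favour of liraglutide and 126 patients per arm (140 less 10%). SE = 1.5 × √(2/126) = 0.189, and 0.10 / 0.189 = 0.529. The critical value falls from 1.645 to 1.116, so the one-sided error at the margin rises from 5% to 13.2%. A shift the other way would make non-inferiority harder to show.

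**5. Does an all-randomised analysis need more patients?** Exact t power with the plan's inputs is 87.2% at 140 per arm and 84.0% at 126 per arm. Both exceed 80%.

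**The case against.** The strongest reply is that little may be lost in practice. The Flow Chart puts randomisation and drug dispensing at the same baseline visit before discharge, and Follow-up Care adds a call to check that medication is available and correctly taken. If receiving medication means having it dispensed, almost everyone randomised would qualify. This stands as an argument about size. It does not supply the missing rule, because the plan never says whether receipt means dispensed or injected.

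Three stronger readings are tempting, and the documents do not support them.

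- A reader might infer that the plan permits dropping up to 15% of randomised patients. That figure requires all 330 recruited patients to be randomised, which is nowhere stated. Nor is it a maximum, since 380 would give 26.3%.
- A reader might infer that recruiting 330 breaches the no-replacement rule. Setting a larger recruitment total in advance is not replacement, and 330 recruited can be consistent with 280 randomised. The firm contradiction is the 380.
- A reader might infer that staff see results by arm while enrolment is open. Open label means that assignments are known. No arm-level summaries or interim looks are described.

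The fall from 280 to 252 with 10% attrition is also no defect, because 126 per arm still exceeds the 124 the plan asks for.

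Finally, in a non-inferiority trial, including patients who never took the drug can pull the arms together and favour the hoped-for conclusion. That objection stands, and it determines the form of the fix.

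**Conclusion.** The point holds in a limited form. The only analysis population the plan describes depends on an event after open-label assignment, no all-randomised set is named, and the totals conflict: 380 analysed cannot hold with 280 randomised and no replacement, and 330 recruited is not linked to a randomised number. The share of randomised patients who could be left out is therefore undetermined, at 0%, 15.2% or 26.3% according to which total is randomised.

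The HbA1c shift of 0.025 to 0.15 and the 13.2% error are illustrations. They rest on assumed rates of non-starting, assumed HbA1c in non-starters and, for the error, an assumed direction. The documents establish none of these, and dispensing at baseline suggests non-starters may be few. The plan should be changed because the rule is missing and cheap to supply. There is no evidence that the comparison will be biased.

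**What to change.** - Correct the 380. State one number each for recruited, randomised, treated and analysed, and use them consistently in Study type, Study Groups, Study population, Rationale for Study Population, Sample Size and Power Calculations, and the Study Schedule. Say when a patient counts as recruited.
- End enrolment on the number randomised, so that the no-replacement rule can be kept as written.
- Make the main analysis all randomised patients in their assigned arm, whether or not drug was started, and say that withdrawn patients remain in it.
- Keep non-starters in the telephone calls and the week-4, week-12 and week-26 visits already scheduled, so that their HbA1c is measured.
- Define receipt of study medication as either dispensed or injected. Report the treated set beside the main analysis, and require the non-inferiority conclusion to be consistent in both.

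The cost is wording, one additional analysis and a slight dilution of the on-drug contrast, which the treated set shows separately. No visits are added to the existing schedule, and no larger sample is needed under the plan's own inputs.
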